1.1 Trial registration number: 91977441

This SAP is based on protocol version 10.0 (date 06/06/2024)

1.2 SAP revision history

		evision mistory			
Protocol version	Updated SAP version no.	Section number changed	List of changes from previous version/protocol	Author of change	Date
4.0	0.1		Initial draft started	CM	01/07/2020
4.0	0.2	all	commented and added on all sections of the SAP	ТН	20/08/2020
4.0	0.3	all	Continued progress on SAP; focus on analysis section 5	СМ	21/08/2020
4.0	0.4	Analysis / outcomes	Focussed again on section 5	СМ	28/08/2020
4.0	0.5	analysis/outcomes	Focus on updating outcomes, and adding information based on study group feedback for missing data/follow-up	СМ	17/09/2020
4.0	0.6	All	Added section 5.10, 6.1, 6.2. Amended various other sections	TH	22/09/2020
6.0	0.7	All	Added to sections on routine maternity data, updated data cleaning and sensitivity analyses section and amended various other sections	СМ	28/09/2020
6.0	0.8	All	Began addressing TSC independent statistician (LA) comments about SAP	СМ	08/12/20

			and continuing to update		
6.0	0.9	All	Filled in some additional information based on further feedback from study team. Added notes about multiple pregnancy analysis and looked further into compliance	СМ	12/05/2021
8.0	0.91	all	Comments on primary outcome analysis and estimands framework.	OQ	03/2022
8.0	0.92	all	Incorporate the learning from reviewing the data to produce the data snapshot; refine the definition of the primary and SVB outcome measures; describe a strategy for using data affected by the pandemic and create template tables.	OQ	23/09/2022
8.0	0.93		Change in the definition of the primary outcome; change in the study population; consideration added for secondary outcomes.	OQ	24/07/2023
8.0	0.94		Change after [name]'s review.	OQ	21/09/2023
9.0	0.10		Change after [name]'s review.	OQ	11/01/2024
9.0	0.11		Development of the SAP following meetings	OQ	13/05/2024

9.0	0.12	Update after comments from trial team	OQ	03/06/2024
10.0	0.13	Update after comments from senior statistician	OQ/TH	01/07/2024
10.0	1.0	Sign off		01/07/2024

^{*}If the SAP has been published, indicate which version.

1.4 Timing of SAP revisions in relation to unblinding of data/results

This document has been developed prior to examination of unblinded trial data by those contributing.

1.5 Analysis software

All analyses and data presentation described in this document and will be carried out using Stata version 18.0 or later unless otherwise specified.

1.6 Remit of SAP

REACH is a programme grant. This SAP covers outcomes from work package 3 (Pregnancy Circles Trial). This plan is intended not to change or contradict the general aims of the protocol, but rather expand on them. In the event of a discrepancy the analyses described here will supersede those in earlier documents.

2. Background and trial design

Study objectives	This trial study objectives are as follows:
	a. To assess whether Pregnancy Circles (group-based antenatal
	care) improves the health of babies compared with the standard
	individual model of antenatal care.
	b. To assess whether attending Pregnancy
	Circles improves maternal outcomes such as empowerment
	and post-natal depression, as well as increasing women's
	satisfaction with antenatal care.
	c. To assess cost-effectiveness, intervention mechanisms, and
	acceptability of group-based antenatal care to women and
	staff and issues relevant to future sustainability and wider
	implementation in the NHS.
Study design	Individually randomised, parallel group, randomised controlled
	superiority trial with integrated process and economic evaluations
Setting	Multi-centre study across 14 NHS Trusts, namely Barts Health NHS
	Trust, Whittington Hospital NHS Trust, Lewisham & Greenwich NHS
	Trust, West Hertfordshire NHS Trust, East Suffolk and North Essex NHS
	Foundation Trust, Princess Alexandra Hospital NHS Trust,
	Worcestershire Acute Hospitals NHS Trust, Mid and South Essex NHS
	Foundation Trust, Ashford and St Peter's Hospitals NHS Foundation,
	East Sussex Healthcare NHS Trust, Lancashire Teaching Hospitals NHS
	Foundation Trust, Surrey and Sussex Healthcare NHS Trust, Epsom &
	St. Helier University Hospitals NHS Trust and Royal Free London NHS
	Foundation Trust
Participants	Women who are currently pregnant and registered for antenatal care
	with the included NHS Trust maternity services, whose estimated due
	dates fit with the proposed group start dates, and who live within the
	usual working areas of these services
Interventions	Intervention
interventions	Pregnancy circles consisting of 8-12 pregnant women, facilitated by
	two midwives (and supplemented with interpreters and/or other
	support staff as appropriate). There will be a total of eight antenatal
	group sessions each of which will last for approximately two hours.
	The first part of each session will involve "self-care activities" (ex.
	Women will be encouraged to take an active part in their antenatal
	care by testing their own urine, taking their own/each other's blood
	pressure and writing the results in their notes). Following these
	checks, the sessions will involve short one-to-one sessions with one of
	the midwife facilitators for individual health checks (ex. Abdominal
	pain) which will take place on a mat in the corner of the room while
	the rest of the group has group discussion facilitated by the second
	midwife. Women will be allowed to request more privacy for one-to-
	one time. The women in the group will also be invited to one post-
	natal reunion session.
	Control
	Usual antenatal care in the maternity service

Primary outcome	A "Healthy Baby" composite outcome consisting of the 4 following
measure(s)	components:
	 Live baby (i.e. no stillbirth after 24 completed weeks of pregnancy, no miscarriage before 24 completed weeks and no neonatal death within 28 days of the birth) Born at term (≥ 37 weeks + 0 days) Appropriate weight for gestational age (GROW centile>9.99 & <90.01) Not admitted to a neonatal care unit (which includes: Intensive Care Unit, SCBU and High Dependency Unit. But NOT transitional care)

3. Outcome Measures

3.1 Timing of outcome measures

Data on the various outcome measures used in this study will be collected either at baseline (recruitment; during the first antenatal booking appointment/first dating-scan appointment), first follow-up (35-weeks gestation), birth (routine maternity data) or second follow-up (3-months postnatal) or a combination of these time points. The table below shows the outcomes, the validated scales/measures which are being used where appropriate, and the specific time points when outcome data will be collected.

Outcome measure and data collection timing

Outcome	Validated measure (where applicable)	Baseline	First follow up - 35 weeks gestation	Birth – routine maternity data	Second follow up - 3 months postnatal
Live baby				√	
Born at term				✓	
Appropriate weight for gestational age	GROW centile >9.99 & <90.01			✓	
Not admitted to a Neonatal Care Unit				✓	
Spontaneous vaginal delivery (SVD)				√	~
Women's empowerment	Pregnancy-related Empowerment Scale (PRES)		√		
Women's satisfaction with maternity care	Friends and family test		✓		√
Attendance at antenatal care			√	√	
Social support	The Duke-UNC Functional Social Support Questionnaire	✓			✓
Self-efficacy	Pearlin Mastery Scale	√	✓		√

Prenatal stress	Revised prenatal distress scale	√	√		
Caesarean delivery				√	√
Infant birth weight (g)				1	
Place of birth				√	
Breast feeding initiation					✓
Breast feeding continuation and exclusivity					√
Postnatal depression	Edinburgh Postnatal Depression Scale (EPDS)				√
Health Literacy	Health Literacy Questionnaire (HLQ) (1 domain)		√		
Postnatal symptoms	(NPEU checklist)				✓
Emotional wellbeing	Short Warwick- Edinburgh Mental Wellbeing Scale (SWEMWBS)	√	✓		✓
Health related quality of life	EQ5D-5L	√	√		✓
Continuity with care			√		
Choice in care			√		√
Involvement in care					√
Preparedness for labour and birth			√		√
Confidence in caring for baby after birth					√
Immunisation					√

Additional			,
measures of		,	√
satisfaction with		V	
care			

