3.2 Primary outcome

The "healthy baby" composite consists of the following 4 components:

- 1. Live baby (i.e. no pregnancy loss before 24 completed weeks, no stillbirth after 24 completed weeks of pregnancy and no neonatal death within 28 days of the birth)
- 2. Born at term (≥ 37 weeks + 0 days)
- 3. Appropriate weight for gestational age (GROW centile >9.99 & <90.01)*
- 4. Not admitted to a neonatal care unit (which includes Intensive Care Unit, SCBU and High Dependency Unit, but NOT transitional care)

A baby is considered a "healthy baby" only if the answer to all above questions is "yes", otherwise "no" (binary outcome measure). The primary outcome will be considered missing if any of its components are missing apart from the following exception: If Live baby is recorded as 'no' then the healthy baby outcome is 'no' regardless of whether other components are missing.

* The GROW centile macro version 8.0.6.2 will be used for component 3. Appropriate weight for gestational age. It is multidimensional and includes: maternal height and weight, ethnic origin, parity at booking, gestational age, baby alive (yes/no), baby gender and weight (g).

Note: at the grant application stage, the secondary outcome, spontaneous vaginal delivery (SVD) was defined as the primary outcome for the trial. However, following advice from and discussion with various stakeholders the "healthy baby" composite outcome was deemed a more suitable primary outcome for this project and chosen prior to commencement of the trial.

3.3 Secondary Outcomes*:

- 1. Spontaneous vaginal delivery (SVD)** defined as a woman who delivers vaginally (binary: for SVD, yes favoured)
- 2. Women's empowerment using pregnancy-related empowerment scale (continuous: sum of individual items with scores ranging from 16-64; higher scores are favoured)
- 3. Women's satisfaction with maternity care using *NHS* Friends and family test (continuous: score on one question with scores ranging from 1-5; lower scores favoured)
- 4. Breast feeding initiation (binary: did mother ever initiate breastfeeding, yes favoured --> however, possible different responses for descriptive analysis)
- 5. Mental wellbeing using Short Warwick-Edinburgh Mental Wellbeing Scale (continuous: total score ranges from 7-35, higher scores indicate higher positive mental wellbeing)

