- 6. Live baby (i.e. no pregnancy loss before 24 completed weeks, no stillbirth after 24 completed weeks of pregnancy and no neonatal death within 28 days of the birth) using health records (binary: yes favoured)
- 7. Born at term (37 weeks + 0 days and above) using health records (binary: yes favoured)

- 8. Appropriate weight for gestational age (GROW centile >9.99 & <90.01) using health records (binary: yes favoured)
- 9. Not admitted to a neonatal care unit (which includes Intensive Care Unit, SCBU and High Dependency Unit, but NOT transitional care using health records binary: yes favoured)
- * Those for whom the primary outcome composite healthy baby variable is 'no' will inevitably have a lower response rate for the first follow up questionnaire. This is because the composite includes whether a baby is alive and born at term (i.e. at 37+ weeks gestation). Participants who have experienced pregnancy loss (baby alive = no) are not sent the first (or second) follow up questionnaire. Participants who deliver prematurely (<35 weeks) will not have had the opportunity to complete the first follow up questionnaire before delivery and are unlikely to complete it after. Analyses of variables collected via the follow up questionnaire, such as empowerment, satisfaction with care, self-efficacy, pre-natal stress, health literacy and emotional well-being, will acknowledge the exclusion of these groups, particularly if it is found that the intervention does have a significant effect on the primary outcome.
- ** Routine data will be used as the default source of data for SVD. We will use second follow-up SVD data only if routine data values for a participant are missing.

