4.3 Blinding

Participants and maternity staff will be unblinded to allocations, along with the researchers conducting the process evaluation observations and interviews. However, data informatics staff supplying outcome information from electronic records and researchers accessing paper records for outcome information will be blinded to allocation. Furthermore, all individuals contributing to the analysis plan and those conducting the analysis at the PCTU will be blinded to intervention allocation until the formal SAP has been signed off and the database locked for analysis.

5. Analysis methods

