5.1 Data cleaning process

Blinded data cleaning has been an ongoing process for the routine maternity data which includes the primary outcome amongst other data related to birth. These data were sent in excel files by sites and data cleaning included range, logical and consistency checks and identifying unreported Serious Adverse Events as defined in the protocol. The process of creating queries has been handled with Stata. Data cleaning reports were then sent to the trial manager to communicate with sites for data correction to ensure the quality of the data before it is locked for the final analysis. A summary of issues identified prior to sign off of the SAP is provided in Appendix Table 17

Data collected on REDCap are self-reported questionnaires that patients have completed throughout the trial. As it was not possible to get back to patients to eventually amend their responses, limited data cleaning is possible on these data. Consistency checks described below will be made and summarised in a table in an appendix to the statistical analysis report.

- 1) Consistency of English level between Randomisation data and baseline questionnaire.
- 2) Check that all randomised participants who have not withdrawn before randomisation have correctly been assigned to a pregnancy circle.
- 3) Consistency check: estimated delivery date should be equal to confirmed delivery date more or less 4 months.

- 4) If AE/SAE has a start date then there should be a description.
- 5) End date of AE/SAE must be equal or greater than start date.

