No 3 months		
Missing		
How many midwives did you have during		
care? (week 35)		
1-2		
3		
4+		
Don't know		
Missing		
Do the midwives you saw got to know you		
and remembered you and your progress?		
(week 35)		
Very satisfied		
Quite satisfied		
Not at all satisfied		
Don't know/can't remember		
Missing		
Do you feel that midwives have been		
sensitive to your cultural and/or language		
needs? (week 35)		
Yes		
Definitely		
Yes, a little		
No, not at all		
Don't know/can't remember		
Missing		
Were you offered any of the following		
choices about where to have your baby?		
(week 35 & 3 months pp)		
A choice of different hospitals		
In a midwife-led unit or a birth centre		
In a consultant-led unit		
At home		
I was not offered any choices		
I was not offered any choices due to medical reasons		
Don't know		
Missing		
Were you involved enough in decisions		
about your care? (3 months pp)		
Yes		
Always		
Yes – sometimes		
No and I wanted to be		

No and I did not want to be		
Don't know		
Missing		
How prepared did you feel for labour and		
birth? (Week 35 & 3 months pp)		
Very well		
Quite well		
Not very well		
Not at all well		
Missing		
How well did you manage during labour?		
(Week 35 & 3 months pp)		
Very well		
Quite well		
Not very well		
Not at all well		
Missing		
How confident did you feel about caring for		
your baby in the first week after the birth?		
(3 months pp)		
Very confident		
Fairly confident		
Not very confident		
Not at all confident		
Don't know/can't remember		
Missing		
Have you received enough help and advice		
from a midwife and/or health visitor about		
your baby's health, care and progress? (3		
months pp)		
Yes, definitely		
Yes to some extent		
No, and I wanted help/advice		
No, but I did not need any		
Don't know		
Missing		

Table 5. Descriptive table of Breast feeding initiation and continuation

	Usual care (N=)	Pregnancy circle (N=)	Total (N=)
Outcome	N participants (%)	N participants (%)	
Birth:			
Breast feeding method			
Breastfeeding exclusive			
Artificial exclusive			
Mixed breast and artificial			
Other			
Not applicable			
Not collected			
Missing			
First few days after the birth:			
What type of milk			
Only breastmilk			
Only formula milk			
Breast AND Formula Milk			
Missing			
Month 3 post-partum:			
What type of milk			
Only breastmilk			
Only formula milk			
Breast AND Formula Milk			
Missing			

Table 6. Protocol deviations summary

	Usual care (N=)	Pregnancy circle (N=)	Total (N=)

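### Table 3.1 sources breastfeeding initiation only from the 3-month questionnaire, while Table 5 expects a feeding method at birth; the two need reconciling with a source rule

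*SAP*

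**What the plan says.** Section 3.3, item 4 defines the outcome as "Breast feeding initiation (binary: did mother ever initiate breastfeeding, yes favoured" and names no data source. Items 6 to 9 of the same list, by contrast, state that health records are used.

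Table 3.1 has a row for "Breast feeding initiation" and ticks it at the second follow-up only. Section 3.1 gives the later collection points as "birth (routine maternity data) or second follow-up (3-months postnatal"), so birth as a time point means the routine record. Section 5.1 describes the questionnaire source: "Data collected on REDCap are self-reported questionnaires that patients have completed throughout the trial".

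Section 8.4 contains "Table 5. Descriptive table of Breast feeding initiation and continuation". It has three blocks: birth, the first few days after the birth, and month 3 post-partum. The birth block is coded exclusive breastfeeding, exclusive artificial, mixed, other, not applicable, not collected and missing.

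For SVD, a footnote to section 3.3 sets an order of sources: "Routine data will be used as the default source of data for SVD", with the second follow-up used only where the routine value is missing. Initiation has no such rule.

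Section 5.5 makes all main analyses complete-case, and section 5.10 assumes data missing completely at random. The multiple imputation in section 5.16.1 covers the primary outcome, and Table 11 adds SVD. Initiation is in neither.

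**The concern.** Whether breastfeeding was started is settled at or soon after birth. If it is read only from a questionnaire three months later, every woman who does not return that questionnaire drops out of the analysis, even if her feeding method was recorded at birth. Responders may differ from non-responders in feeding, and response may differ by arm. Nothing in the plan would reveal the effect of this on initiation.

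The second problem is ambiguity. An analyst working from table 3.1 and one working from Table 5 could derive different versions of the same secondary outcome, on different sets of women. That choice should be fixed before the unblinded data are examined.

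**Working it through.** The SAP states no figure for breastfeeding initiation, so there is none to reproduce. The check is mainly one of reading.

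**1. Which source does the plan give?**

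| Place in the SAP | What it shows for initiation |
|---|---|
| Table 3.1 | Second follow-up only; routine birth column empty |
| Section 3.3, item 4 | No source |
| Table 2 | Continuation and depression are labelled as month 3 outcomes; initiation has no time label |
| Table 5 | Birth block, first-few-days block and month 3 block, with no statement of which defines the binary outcome |

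The only stated source is the 3-month questionnaire, and Table 5 is not reconciled with it.

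**2. Is the birth block routine data?** Table 5 does not label its source. Two observations point the same way. Section 3.1 lists no questionnaire at birth and equates that time point with routine maternity data. The birth block also uses record-style codes (not applicable, not collected), while the other two blocks ask what type of milk was given. The inference is reasonable but remains an inference.

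**3. What happens to non-response?** In each arm let r be the response proportion and g the initiation rate in responders minus that in non-responders. The responder rate exceeds the rate in all women by g × (1 − r). The bias in the complete-case risk difference (circles, PC, minus usual care, UC) is therefore

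g_PC × (1 − r_PC) − g_UC × (1 − r_UC).

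With the same g in both arms this becomes g × (r_UC − r_PC). The SAP gives neither r nor g, so the following values are assumptions for illustration only:

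| g, both arms | r_PC | r_UC | Bias in risk difference |
|---|---|---|---|
| 10 or 20 points | 70% | 70% | 0 |
| 10 points | 75% | 65% | 0.10 × (0.65 − 0.75) = −1 point |
| 20 points | 75% | 65% | 0.20 × (0.65 − 0.75) = −2 points |
| 10 points | 80% | 60% | 0.10 × (0.60 − 0.80) = −2 points |
| 20 points | 80% | 60% | 0.20 × (0.60 − 0.80) = −4 points |

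The signs reverse if usual care responds better.

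**4. What happens to precision?** Under a record-first rule with the questionnaire as fallback, the women analysed are those with a usable record plus those without one who answered the questionnaire. Leaving aside women coded not applicable, that set cannot be smaller than the questionnaire responders alone. How much larger it is depends on record completeness, which the SAP does not give.

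**The case against.** The strongest reply is that the documents support an unreconciled source and little more. Most of this stands.

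- **Deliberate choice.** A reader might infer that the team knowingly preferred the weaker source and set aside data already extracted. The SAP does not show this. Item 4 names no source, Table 2 leaves initiation without a time label, and an empty dummy table shows that a field is expected, not that it is held or complete. The protocol may also say more on sources.
- **Blinding.** A reader might infer that the record gives a blinded measurement. Section 4.3 does blind those supplying or extracting records, but it also says "Participants and maternity staff will be unblinded to allocations". If maternity staff make the feeding entry, they know the arm.
- **Demonstrated bias.** No response rate is given, and recall of ever having started breastfeeding may carry little error. Women with pregnancy loss are not sent the questionnaire, but most of them could not have initiated, so ordinary non-response is the main issue.
- **A broken convention.** SVD is not the only outcome held in both sources. Table 3.1 ticks caesarean delivery at birth and at second follow-up, and no order of sources is stated for it. The SVD footnote is a useful model, not a general rule that initiation alone breaks.
- **Construct.** The outcome is "did mother ever initiate breastfeeding, yes favoured". A birth entry is a snapshot. A woman recorded as exclusively artificial at birth may breastfeed days later, and a record-first rule would code her as not initiating.

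The last point does not argue for leaving the source unstated, but it does mean that a record-first rule needs a sensitivity analysis that lets either source count. What survives all of these replies is that table 3.1, taken literally, drops non-responders from a secondary outcome for which a birth-record field is evidently expected.

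**Conclusion.** The point holds as a cheap improvement, not as a demonstrated bias. Table 3.1 and Table 5 are not reconciled, and the plan does not say which source defines breastfeeding initiation. As written, the analysis is confined to questionnaire responders under an assumption of data missing completely at random, with no missing-data sensitivity analysis for this outcome.

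Neither the loss of precision nor any bias can be sized from the SAP. Under the assumed inputs above, the bias ranges from nil to about 4 points in absolute value; this illustrates the mechanism and is not an estimate for this trial. The conclusion rests on one inference, that Table 5's birth block is the routine record. If that is wrong, the need to state the source of that block and of the binary outcome remains, but the record-first remedy would depend on whether such a field exists.

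**What to change.** 1. In table 3.1, tick routine birth data for breastfeeding initiation as well as the second follow-up, and label the source of each block in Table 5.
2. Extend the SVD source rule to initiation. Take the birth record first: exclusive or mixed breastfeeding is yes, exclusive artificial is no. Where the record is missing, other or not collected, use the second follow-up item on the first few days. State how the not-applicable code is handled.
3. Add two sensitivity analyses: (a) self-report only, and (b) yes if either source shows any breast milk. The second protects the ever-initiated definition against feeding begun after the birth entry.
4. Report by arm how many women are classified from each source and how many remain missing.

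If the birth block is the routine field, the cost is SAP wording, one derivation and two short sensitivity analyses, with no new data collection. The downside is that the birth record may have gaps and may miss feeding begun later; the fallback and analysis (b) address these as far as questionnaire responses allow.
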